7.2.5. Expected drop-out rate

Expected drop-out rate is set as 10% in this study.

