7.4. Criteria for terminating the trial based on the statistical reasons and justification

The interim analysis for study early termination is not planned, so this section is not applicable.

7.5. Statistical method of all data, together with the handling method of missing, unused and wrong data (including discontinuation and withdrawal) and unreasonable data

Analysis of demographic characteristics, baseline data and operation information

[figure not shown]
Demographics, baseline characteristics and procedural information will be

analyzed in the full analysis set (FAS) and the safety analysis set.

[figure not shown]
The descriptive statistics of continuous variables will include the number of subjects with valid data, number of missing, mean, standard deviation, quartiles, minimum and maximum. The descriptive statistics of categorical variables will include the frequency and percentage. The number of missing will not be included in the denominator for percentage calculation.

The data analysis plan will be documented in detail in the Statistical Analysis Plan.

CCI

CCI

Analysis of secondary endpoints

All secondary endpoints will be analyzed on the FAS.

- Acute Procedural Success: the number and percentage of patients with acute procedural success will be calculated, and the two-sided 95% confidence

interval (CI) will be calculated by the exact (Clopper-Pearson) test method.

- Acute reconnection identified by adenosine/isoproterenol challenge among all clinically relevant targeted PVs and by subject: the number and percentage of PVs/patients with acute reconnection will be calculated, and the two-sided 95% CI will be calculated by the exact (Clopper-Pearson) test method.
- Rate of PV ablation by a non-study catheter (touch-up) among all clinically relevant targeted PVs and by subject: same statistical analysis method as acute reconnection.
- Rate of repeated ablation within the 12M FU period: same statistical analysis method as acute procedural success.

The secondary endpoints will not be used for statistical inference, but for descriptive purposes. Therefore, multiplicity will not be adjusted.

Analysis of safety endpoints

The safety endpoints will be analyzed in the safety set.

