AEs will be summarized, including the number of AEs and the number and percentage of subjects experiencing any AEs. All PAE, SAEs and all procedure-/device-related AEs will be analyzed in same way. The severity, relationship, AE treatment intervention, seriousness and outcome of all AEs will be described.

In addition, all AEs, PAE, serious and non-serious AEs will be summarized according to the system organ classification and preferred terms of MedDRA, and a list will be generated, including but not limited to subject identification number, age, AE term, start and end time (corresponding duration post procedure), severity, relationship, AE treatment intervention, seriousness, and outcome.

Handling of missing value

Subjects will be contacted by different means, such as by telephone, to avoid missing value.

For the primary endpoint, missing primary endpoint data of the subjects in the FAS will be excluded from the final primary effectiveness analysis as described in “Primary analysis of primary endpoint” of Section 7.5.

For those who had the investigational device inserted but not ablated, they would be replaced, and new subjects should be screened and enrolled to ensure total 110 evaluable non-roll-in subjects.

For baseline information, operational information, or secondary endpoints, all observed data will be used for analysis. Missing data imputation will not be

performed.

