2.1 General rules

All statistical analyses will be performed based on SAS® 9.4 M6 version.

Statistical analysis will be performed mainly using descriptive statistics. The number of cases, mean, standard deviation (SD), median (first quartile Q1, third quartile Q3), minimum and maximum will be used for continuous variables; and the number of cases and percentage will be calculated for categorical variables. The number of missing will not be included in the denominator for percentage calculation. Table 1 shows the number of decimal places retained for statistical parameters.

Table 1. Number of decimal places retained for statistical parameters

| Statistical magnitude | Number of decimal places retained |
|-----------------------|-------------------------------------------------------------------------------------------------------------------------------------|
| Mean, Median, Q1, Q3 | Retain 1 more decimal place than the original data, up to a maximum of 4 decimal places. |
| SD, 95% CI | Retain 2 more decimal place than the original data, up to a maximum of 4 decimal places. |
| Maximum, Minimum | Retain the same number of decimal places as the original data, up to a maximum of 4 decimal places. |
| Percentage | Retain one decimal place; if the percentage reaches 100%, it is expressed as “100”, if the percentage is 0, it is expressed as “0”. |
| P value | Retain 4 decimal places; when all 4 decimal places are 0, it is expressed as $P < 0.0001$ |

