2.3.5 Rules for missing data processing

In the final analysis, a sensitivity analysis for the primary endpoint, missing data will be imputed using multiple imputation.

No imputation will be performed for the missing data on baseline information, procedural information, or secondary effectiveness endpoints.

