3.2.2 Analysis of secondary effectiveness

All secondary endpoint analyses will be based on RI AT, FAS, and SS AT.

- Acute Procedural Success: the number and percentage of patients with acute procedural success will be calculated, and the two-sided exact 95% confidence interval (CI) will be calculated by the Clopper-Pearson method.
- Acute reconnection: the number and percentage of PVs/subjects with acute reconnection will be calculated, and the two-sided exact 95% confidence interval (CI) will be calculated by the Clopper-Pearson method.
- The number and percentage of PVs/subjects requiring touch-up with a non-study catheter among ablation procedures (including index and repeat ablation procedures); the two-sided exact 95% confidence interval (CI) will be calculated by the Clopper-

Pearson method. Wherein, repeat ablation is defined as any ablation procedure performed after the index procedure, including those recorded during scheduled and unscheduled visits.

- The number and percentage of subjects with repeat ablation procedures during the 12-month follow-up period will be summarized, and the two-sided exact 95% confidence interval will be calculated by the Clopper-Pearson method. The time of repeat ablation (during blanking period, during effectiveness assessment period) and the proportion of PVs/subjects that recovered will be presented. The types of arrhythmias treated with repeated ablation will be presented. Wherein, repeat ablation is defined as any ablation procedure performed after the index procedure, including those recorded during scheduled and unscheduled visits.

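### The 12-month repeat-ablation rate is a crude percentage with no rule for subjects who leave early, so it can miss the 12-month risk in either direction by about 5% of its value

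*SAP*

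**What the plan says.** Repeat ablation within 12 months is a named secondary effectiveness endpoint (SAP 1.2.2). SAP 3.2.2 plans: "The number and percentage of subjects with repeat ablation procedures during the 12-month follow-up period will be summarized". A two-sided exact 95% Clopper-Pearson interval is attached, and repeats are split by blanking or evaluation period. Protocol 7.5 agrees: "Rate of repeated ablation within the 12M FU period: same statistical analysis method as acute procedural success".

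The rules that bear on incomplete follow-up are general ones:

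- Analysis sets, SAP 3.2.2: "All secondary endpoint analyses will be based on RI AT, FAS, and SS AT".
- Denominators, SAP 2.1 (Protocol 7.5 has the same rule): "The number of missing will not be included in the denominator for percentage calculation".
- Missing data, SAP 2.3.5: "No imputation will be performed for the missing data on baseline information, procedural information, or secondary effectiveness endpoints". Protocol 7.5 adds: "For baseline information, operational information, or secondary endpoints, all observed data will be used for analysis".
- Attrition, Protocol 7.2.5: "Expected drop-out rate is set as 10% in this study". Under Protocol 6.1.4.3, subjects who stop early are assigned to analysis sets by the set definitions and are not replaced.

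The text of SAP 3.2.2 is not blacked out. It contains no censoring rule, no time-to-event estimate and no denominator for this endpoint. Protocol 7.5 states that secondary endpoints are descriptive and not used for inference.

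**The concern.** The method is borrowed from acute procedural success, an outcome known for every treated subject when the procedure ends. Repeat ablation builds up over a year. A subject last seen at month 4 without a repeat is neither a full-year success nor wholly uninformative, and a simple percentage has to treat that subject as one or the other. Each choice moves the figure away from the 12-month risk. Because the plan does not choose, the choice could be made after the data are seen.

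What is at stake is a descriptive figure in a registration study with no concurrent control. Readers will take a 12-month rate as an estimate of 12-month risk.

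**Working it through.** **The plan's own figures.** The documents give no expected repeat-ablation rate, so there is no planned figure to reproduce for this endpoint. The 10% attrition is the one used for sample size in SAP 1.3.3: 110 / 0.90 = 122.2, rounded up to 123, as stated.

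**Assumptions.** True 12-month risk p between 5% and 20% (assumed); drop-out d = 10% from the plan, varied to 5% and 15%; constant hazards of repeat ablation and of exit; exit unrelated to repeat ablation.

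**Formulas.** Let λ = −ln(1−p) and μ = −ln(1−d).

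- Repeat seen before exit: A = λ/(λ+μ) × [1 − (1−p)(1−d)]
- Exit without a repeat: B = μ/(λ+μ) × [1 − (1−p)(1−d)]
- Reading 1, leavers kept as event-free: A
- Reading 2, event-free leavers dropped and earlier repeats kept: A / (1 − B)
- An estimate censored at exit targets p.

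**Central case, p = d = 10%.** λ = μ = 0.1054, and 1 − 0.9 × 0.9 = 0.19, so A = B = 0.5 × 0.19 = 0.095. Reading 1 gives 9.5%. Reading 2 gives 0.095 / 0.905 = 10.5%.

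**Other true rates, d = 10%:**

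| True 12-month rate | Reading 1 | Reading 2 |
|---|---|---|
| 5% | 4.75% | 5.26% |
| 10% | 9.50% | 10.50% |
| 15% | 14.26% | 15.71% |
| 20% | 19.02% | 20.90% |

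The shift is about 5% of the rate either way, or roughly 0.25 to 1 percentage point.

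**Other drop-out levels, p = 10%.** At 5% drop-out: 9.75% and 10.24%. At 15%: 9.24% and 10.78%.

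**Other exit and event patterns, p = d = 10%.**

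- Exit times uniform over the year: reading 1 is 0.9 × 0.10 + 0.1 × 0.051 = 9.51%, where 0.051 is the average cumulative risk at exit. Almost unchanged.
- Repeats only after day 90: the average cumulative risk at exit falls to about 0.038. Reading 1 is 0.09 + 0.0038 = 9.38%. Reading 2 is 0.0938 / (1 − 0.1 × 0.962) = 10.4%.
- All exits on day 0: reading 1 is 0.9 × 0.10 = 9.0%; reading 2 is 0.09 / 0.90 = 10%.

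**Against sampling error.** Take 12 subjects with a repeat and 123 subjects in the set. (The set definitions in SAP 2.2 are blacked out, so 123 is illustrative.)

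- 12/123 = 9.8%, exact 95% interval 5.1% to 16.4%, width 11.3 points.
- With 12 event-free leavers removed, 12/111 = 10.8%, interval 5.7% to 18.1%.

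Under reading 1 at 10% drop-out, the exact interval with n = 123 still covers the true rate 96.3% to 96.8% of the time for true rates of 5% to 20%. If every leaver exits on day 0, coverage is about 94% to 97%.

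**The case against.** **Direction.** A reader might infer that the percentage counts early leavers as free of repeat ablation and so flatters the device. Repeat ablation is a recorded event, and events over everyone in the set is a common way to program such a line. But no section sets that denominator. SAP 2.1 removes missing values from percentages, Protocol 7.5 uses observed data only, and SAP 3.1.4 names the whole analysis set as denominator for medical history, which SAP 3.2.2 does not do. If an event-free leaver is missing under SAP 2.1, the bias runs upward, against the device. A fixed downward bias is not supported.

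**Size of the loss.** The 10% is an allowance for the primary endpoint, which depends on ECG and Holter data. Repeat ablation is recorded at follow-up and unscheduled visits (Protocol 6.2 and 6.5.6), and Protocol 6.1.4.3 requires repeated contact attempts, so loss for this endpoint may be lower. That is fair; at 5% drop-out the shift halves.

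**Consequence.** The endpoint has no performance goal and no test, timing by period is already reported, and a count with an exact interval is a legitimate description. The calculation also does not support a claim that the interval fails in practice. All of this stands and limits the point to a small improvement. It does not remove it: a percentage under either reading does not target the 12-month risk when some follow-up is incomplete, and the plan does not say which reading applies.

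**Conclusion.** The point holds in limited form. The planned 12-month figure is a crude percentage whose treatment of early leavers is unstated. It understates the 12-month risk under one reading and overstates it under the other, by about 5% of its value at the planned 10% drop-out. Which way it would go cannot be settled from the documents.

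This rests on an assumed true rate of 5% to 20%, constant hazards, exits spread over the year and exit unrelated to repeat ablation. If subjects with recurrence tend to leave and are re-treated elsewhere, reading 1 could understate by more, and a censored estimate would not fully repair that. The effect is minor, on a descriptive endpoint, and does not touch the primary analysis.

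**What to change.** In SAP 3.2.2:

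- Report as the 12-month rate the cumulative incidence of first repeat ablation at day 365 with a 95% CI, either by Kaplan-Meier with censoring at last contact, or as cumulative incidence with death as a competing event.
- Keep the crude count and percentage as a second line, and state its denominator and how subjects who leave before month 12 without a repeat are counted.
- Show the number still at risk near day 365. The 12-month visit window opens at day 335 (Protocol 6.2), so some subjects who complete the study will have a last contact shortly before day 365.

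The cost is SAP wording and one more standard analysis. No new data appear to be needed: splitting repeats by period already requires their dates, and the completion form is tied to the last completed visit or last data collection (Protocol 6.2, Table 2 footnotes). The downside is that the estimate assumes leaving is unrelated to repeat ablation, which should be stated beside the result.

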3.2.3 Other endpoints

All other endpoint analyses will be based on RI AT, FAS, and SS AT.

- Length of hospital stay for index ablation (days)
- Cardiovascular hospitalization (days)

3.2.4 Exploratory endpoints

- Proportion of patients with long-term effectiveness success with recurrence (AF, AT, AFL) during blanking period.
- Proportion of patients with long-term effectiveness success in single procedure.
- Change in study catheter LA dwell time (min) from the first procedure to the last procedure for surgeons in single-surgeon sites.

3.3 Safety analysis

Unless otherwise specified, all safety analyses will be based on SS.

3.3.1 Adverse Event

Adverse events (AEs) will be coded using MedDRA (V25.1 or higher).

The number of adverse events, the number and percentage of subjects with adverse events will be summarized and analyzed based on the RI AS, FAS and SS:

- Any AE

- Occurrence of AEs within 7 days (early-onset) of initial ablation procedure
- Occurrence of AEs within 8-30 days (peri-procedural)
- Occurrence of AEs >30 days (late onset)
- Mild
- Moderate
- Severe
- PAE
 - Ablation catheter-related
 - Generator-related
 - Ablation procedure-related
- SAE
 - Occurrence of SAEs within 7 days (early-onset) of index ablation procedure
 - Occurrence of SAEs within 8-30 days (peri-procedural)
 - Occurrence of SAEs >30 days (late onset)
 - Mild
 - Moderate
 - Severe
- SAE
 - Leading to death
 - Life-threatening illness or injury
 - Requiring hospitalization or prolongation of existing hospitalization
 - Permanent impairment to the body structure or body function
 - Requiring medical measures to prevent permanent impairment to the body structure or body function
 - Leading to fetal distress, fetal death, congenital abnormality or congenital defect
 - Other
- Serious non-primary AE
 - Occurrence of SNPAEs within 7 days (early-onset) of index

ablation procedure

- Occurrence of SNPAEs within 8-30 days (peri-procedural)
- Occurrence of SNPAEs >30 days (late onset)
- Mild
- Moderate
- Severe

- Non-serious AE
 - Occurrence of non-serious AEs within 7 days (early-onset) of index ablation procedure
 - Occurrence of non-serious AEs within 8-30 days (peri-procedural)
 - Occurrence of non-serious AEs >30 days (late onset)
 - Mild
 - Moderate
 - Severe
- Relationship between AE and procedure
 - Definitely unrelated
 - Unlikely related
 - Possibly related
 - Definitely related
- Procedure-related AEs (including: Possibly related and Definitely related)
 - Mild
 - Moderate
 - Severe
- Procedure-related SAEs
- Relationship between AE and ablation catheter
 - Definitely unrelated
 - Unlikely related
 - Possibly related
 - Definitely related

- Ablation catheter-related AEs (including: Possibly related and Definitely related)
 - Mild
 - Moderate
 - Severe
- Ablation catheter-related SAEs
- Relationship between AE and generator
 - Definitely unrelated
 - Unlikely related
 - Possibly related
 - Definitely related
- Generator-related AEs (including: Possibly related and Definitely related)
 - Mild
 - Moderate
 - Severe
- Generator-related SAEs
- AE outcome
 - Symptoms disappeared without sequelae
 - Symptoms disappeared with sequelae
 - Symptoms ongoing
 - Symptoms recovering/resolving
 - Symptoms aggravated
 - Fatal
 - Other
- Intervention or other treatment measures taken for AEs
 - None
 - Medical therapy
 - DC cardioversion
 - Repeat ablation
 - Procedure

- Other
- AEs leading to the study discontinuation for subjects
- Unanticipated AEs
- AEs leading to death
- Death (type of death, cause of death)

A summary of all PAEs and their CEC-adjudicated relationships will be made in the SS.

The number of AEs, the number and percentage of subjects with AEs will be summarized separately by SOC and PT, as well as by severity (mild, moderate, severe) and by onset period (early, peri-procedural, late) in the SS as follows:

- AE
- PAE
- SAE
- Non-Serious AE

In addition, the number of AEs, the number and percentage of subjects with AEs will be summarized by SOC and PT as well as relationship (procedure-related, ablation catheter-related, generator-related) in the SS as follows:

- AE
- SAE
- non-serious AE
- SNPAE
- Unanticipated AE

The relationship includes: Possibly related and Definitely related.

When an AE is described based on the subjects, if the same AE (as distinguished by MedDRA Preferred Term) occurred more than once during the study for the same subject, the subject will be counted only once. Similarly, if an AE occurred more than once in the same System Organ Class for the same subject, the subject will be counted only once in that System Organ Class.

All AEs will be tabulated, recording the name of AE, preferred term (PT), date of index procedure, start date (postoperative days), end date (postoperative days), severity, whether it is a PAE, whether it is an unanticipated AE, whether it is a SAE, classification of SAE, relationship with the procedure (if related to the procedure, whether it is an index or repeat procedure), related to the IRE Catheter, related to the IRE Generator, actions taken for the AE, outcome, date of death,

etc.

Wherein, Postoperative days = AE start/end date – procedure date

3.3.2 Deficiencies of investigational device

Based on RIAS, FAS, and SS, the number and percentage of deficiencies for the investigational device will be summarized by ablation catheter and generator, respectively, including the type of deficiency, time of occurrence of device deficiency, whether the device is returned to the sponsor, whether it leads to an AE.

A list will be presented by subjects and the investigational device.

3.3.3 Other safety analysis

Subjects' mRS scores and changes from baseline at each visit will be summarized descriptively based on RI AT, FAS and SS AT. Shift tables will be used to summarize the change in mRS score (<2 , ≥ 2) from baseline at each visit.

4 Interim analysis and Data Monitoring Committee (DMC)

[figure not shown]
[figure not shown]

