6.1.4.8. Subject Enrollment Disposition

- Enrolled Subjects: Patients who sign the ICF and meet all eligibility criteria.
- Excluded Subjects: Subjects who are enrolled but never undergo insertion of the study catheter. Excluded subjects will be subjected to safety event reporting between ICF signature and date of exclusion. Enrolled Subjects found to be ineligible prior to insertion of the catheter are also considered as excluded.

- **Evaluable Subjects:** All enrolled subjects who have the study catheter inserted.
- **Discontinued Subjects:** Evaluable subjects but do not undergo ablation (i.e., no energy is delivered with the study catheter).
 - Discontinued subjects will remain in follow-up for 3-months post catheter insertion.
 - If an SAE is reported for a discontinued subject, the subject will be followed until event resolution (with or without sequelae), stabilization, or until the event is adequately explained.
- **Lost to Follow-up Subjects:** Evaluable subjects of which contact is lost after most recent visit (despite 3 documented attempts to contact the subject).
- **Withdrawn / Early Termination Subjects:** Subjects who withdraw consent for study participation or are withdrawn by the investigator, are terminated from the study prior to completion of all follow-up visits.
- **Completed Subjects:** Enrolled subjects who have not been excluded, discontinued, withdrawn, terminated early, or lost-to-follow-up from the study prior to the final study visit.

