6.5.6. Post-Ablation Follow-up Schedule

The subject will be required to complete follow-up visits through 12 months post initial ablation procedure. Follow-up will be done at discharge, 7 day +3 days (phone call or clinic visit), 1 month ± 7 days (phone call or clinic visit), 3 month ±14 days, 6 month ± 30 days and 12 month ± 30 days (clinic visit). Follow-up visit schedule should be based on the date of the index study ablation procedure and will not reset if subject undergoes a repeat AF ablation procedure.

Prior to hospital discharge, the following assessments should be performed:

- Physical exam MUST be performed pre-discharge.
 - If physical exam demonstrates new abnormal neurological findings as compared to the one performed at baseline, a formal neurological consult and examination with appropriate imaging (i.e., DW-MRI) needs to be done to confirm or rule out any suspected diagnosis of stroke.
 - Diagnosis of stroke/CVA must be confirmed by at least one of the following:
 - Neurology or neurosurgical specialist
 - Neuroimaging procedure (MR or CT scan or cerebral angiography)
 - Lumbar puncture (i.e., spinal fluid analysis diagnostic of intracranial hemorrhage)

- Stroke: (diagnosis as above, preferably with positive neuroimaging study)
 - Minor-Modified Rankin score<2 at 30 and 90 days
 - Major-Modified Rankin score≥2 at 30 and 90 days
 - MRS assessments should be made by certified individuals
- Medication regimen (Cardiac, anti-coagulation, PPIs and AE related)
- TTE should be performed to evaluate pericardial effusion
- AEs events
- AF/AT/AFL recurrence
- 12 or 15 leads ECG

At 7 day, 1-, 3-, 6-, 12-month follow-up, and at any unscheduled visits, the following assessments will be performed:

- Physical exam: exam should be performed at all clinical visits (except at 7 day follow-up)
- 12 or 15 leads ECG. Data from 12 or 15 leads ECG recordings will be collected at 3-, 6- and 12-month follow-up visits. ECG data will be collected at unscheduled visits if completed as standard of care.
- 24 Hour Holter: Holter monitor will be used at 3-, 6- and 12-month follow-up visits to monitor the subjects' heart rhythm for 24 hours continuously.
- Cardiac CT/MRA image: Any subjects who have symptoms suggestive of PV stenosis should undergo CT/MRA imaging.
- Adverse Events: AEs must be collected from the time the subject signs the informed consent onwards.

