3.1.3 Demographics and baseline characteristics

Subject demographics and baseline characteristics will be summarized descriptively based on the RI AS, FAS, and SS.

Demographics:

- Age (years)
- Age: < 45 years, [45, 65 years) , \geq 65 years
- Gender (M, F)

Baseline characteristics:

- Height (cm)
- Weight (kg)
- BMI (kg/m²)
- Pulse (bpm)
- Blood pressure systolic/blood pressure diastolic (mmHg)
- mRS score (0, 1, 2, 3, 4, 5, 6)
- CHADS₂ score (points)
- CHADS₂ score (points) (0, 1, 2, 3, \geq 4)
- CHA₂DS₂-VASc score (points)
- CHA₂DS₂-VASc score (points) (0, 1, 2, 3, \geq 4)
- Pre-procedure anticoagulant therapy (Yes, No)
- Pre-procedure left atrial thrombus detection method
- Whether a left atrial thrombus is found (Yes, No)

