4.2 Data Monitoring Committee

This study will have a DMC. The established DMC will review the data and put forward recommendations according to the approved study specific charter.

5 Modifications to the original analysis plan

Version 1.1 (Revision date: April 18, 2024)

1. Two new analysis sets were added for analyzing subjects treated with the investigational device. Analyses related to the effectiveness of the study procedure were required to be based on subjects treated with the investigational device.
 - Safety analysis set as treated (SS AT): It includes all the subjects in the SS who have the investigational devices treated.
 - Roll-in analysis set as treated (RI AT): It includes all the subjects in the RI AS who have the investigational devices treated.
2. The analysis of AEs related to the investigational device was removed as analyses were conducted separately for the study catheter and generator.

6 References

Currently none.

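### SAP 3.3.3 runs the mRS safety summary on as-treated sets, so subjects with the catheter inserted but no energy delivered very probably drop out of the only post-procedure mRS table

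*SAP*

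**What the plan says.** **Population.** SAP 3.3.3 (Other safety analysis) states that "mRS scores and changes from baseline at each visit will be summarized descriptively based on RI AT, FAS and SS AT". It adds a shift table of mRS below 2 against 2 or more, "from baseline at each visit". The rule at the head of SAP 3.3 is "Unless otherwise specified, all safety analyses will be based on SS".

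SAP section 5 (Version 1.1) defines SS AT: "It includes all the subjects in the SS who have the investigational devices treated". RI AT is defined in the same way within RI AS. The reason given there is "Analyses related to the effectiveness of the study procedure were required to be based on subjects treated with the investigational device".

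Protocol 7.1 evaluates safety on everyone who had the catheter inserted or was ablated. Protocol 6.1.4.8 defines Discontinued Subjects as "Evaluable subjects but do not undergo ablation (i.e., no energy is delivered with the study catheter", and keeps them in follow-up for 3 months after insertion.

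**Collection.** SAP 3.1.3 lists "mRS score (0, 1, 2, 3, 4, 5, 6" as a baseline characteristic, summarised on RI AS, FAS and SS. In the protocol, the only timed mRS belongs to stroke grading, for example "Minor-Modified Rankin score<2 at 30 and 90 days" in 6.5.6, repeated in Table 4 of 13.2.1.

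**The concern.** mRS measures neurological disability, which is a safety matter here and not a measure of whether ablation worked. A procedure abandoned after catheter insertion but before energy delivery is one setting in which a neurological complication could arise. Restricting the table to treated subjects removes that group by rule, and the SAP gives no reason for doing so in a safety summary.

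At stake is whether the disability grade of such a subject is shown in any post-procedure summary. There is also a consistency problem. Baseline mRS in 3.1.3 and the baseline column of the shift table in 3.3.3 use different sets, so their denominators will differ if any subject was inserted but not treated.

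The second concern is data. The table asks for a change from baseline at every visit, and the protocol does not schedule the score at any visit.

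**Working it through.** No stated figure is at issue, so the check compares the population rules and then the visit schedule.

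**1. Sets used across the safety section**

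| SAP section | Content | Sets |
|---|---|---|
| 3.3 | Safety default | SS |
| 3.3.1 | Adverse events | RI AS, FAS, SS |
| 3.3.2 | Device deficiencies | RI AS, FAS, SS |
| 3.3.3 | Post-procedure mRS | RI AT, FAS, SS AT |
| 3.1.3 | Baseline mRS | RI AS, FAS, SS |

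Section 3.3.3 is the only safety subsection on as-treated sets. The other places that use them are procedural data, ECG and Holter compliance, secondary effectiveness and hospital stay (SAP 3.1.9 to 3.1.12, 3.2.2, 3.2.3).

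**2. Which sets hold an inserted-but-not-ablated subject?**

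- *SS:* yes, if it follows Protocol 7.1 (inserted or ablated). The formal definition is redacted.
- *SS AT:* very probably no. The protocol synopsis sets inserted and treated apart as alternatives. If SS is inserted or ablated, a treated subset differs from it only by leaving out subjects who received no energy.
- *RI AT:* no for roll-in subjects, by the same reasoning; it draws only on RI AS.
- *FAS:* very probably no. The definition is redacted, but Protocol 7.1 evaluates the primary endpoint on non-roll-in subjects who received ablation energy. SAP 3.2.1 times the FAS analysis by the follow-up of those same subjects. Protocol 7.5 replaces subjects inserted but not ablated.

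Such a subject therefore counts for safety but very probably appears in no set named in 3.3.3.

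**3. Could these subjects have contributed data?** Yes, in part. Three months of follow-up spans day 30 and day 90, when the protocol grades a stroke by mRS. Of the six post-procedure assessments (discharge, 7 days, 1, 3, 6 and 12 months), they could reach the first four. They could not routinely fill the 6- and 12-month rows under any choice of set.

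**4. Is mRS scheduled?**

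| Place in protocol | Routine mRS? |
|---|---|
| Synopsis schedule and Table 2 (6.2) | No row |
| Baseline list (6.4.2) | Not named |
| Discharge and follow-up lists (6.5.6) | Only within stroke diagnosis |
| Stroke criteria (6.5.6; Table 4) | Day 30 and day 90, to grade a stroke |

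Routine mRS is scheduled at 0 of the 6 post-procedure assessments. The protocol also asks that certified individuals score mRS, while the 7-day and 1-month contacts may be by telephone.

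**5. Number affected.** The documents give no count or expected rate of subjects inserted but not ablated, and no expected stroke rate. The number omitted cannot be computed.

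**The case against.** **The default allows exceptions.** The SS rule applies unless something else is specified, and 3.3.3 specifies something else. That stands: 3.3.3 does not breach SAP 3.3. The point is that the exception is unexplained, and the stated reason for the as-treated sets does not cover it.

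**The safety signal is not lost.** A reader might infer that a stroke in a subject who received no energy vanishes from the safety reporting. The documents do not support that. AEs and SAEs are tabulated on SS by severity, onset period and outcome (SAP 3.3.1), all AEs are listed, and SAP 2.3.4 puts all collected data in listings. The CEC-adjudicated PAE summary is also on SS, although Protocol 13.2.1 ties a PAE to an ablation procedure, so classification of such an event is uncertain. What those tables lack is the mRS grade; they use mild, moderate and severe. The mRS table is descriptive and is not a named safety endpoint.

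**Not every stroke before energy delivery is affected.** A reader might extend the point to a stroke during vascular access or transseptal puncture. If the study catheter was never inserted, Protocol 6.1.4.8 classes the subject as Excluded, outside the safety population of Protocol 7.1. Moving from SS AT to SS would not bring that subject in.

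**The data may exist.** A reader might infer that the table would have no planned data behind it. The SAP is built on CRF v3.0, which is not among the documents. The full 0 to 6 scale at baseline suggests there is a field for it, and the protocol's medical history list is open-ended. The supported statement is narrower: the protocol does not schedule routine mRS.

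**Conclusion.** The point holds as a consistency defect of low to moderate priority. A safety summary is run on sets created for effectiveness analyses, out of line with the rest of the safety section and with the baseline mRS table. Subjects inserted but not ablated very probably drop out of the SAP's only post-procedure mRS summary.

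This rests on two inferences, because the definitions are redacted: that treated means energy was delivered, and that FAS is limited to ablated subjects. If treated included insertion alone, SS AT would coincide with SS and nothing would be lost, but the separate set would then have no purpose.

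The effect is limited to one descriptive table. No endpoint, test or adverse event count changes.

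The secondary point also holds within its limits: SAP 3.3.3 assumes mRS at every visit, the protocol does not schedule it, and only the CRF can show what is collected.

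**What to change.** 1. In SAP 3.3.3, replace RI AT and SS AT with RI AS and SS, and keep FAS as supportive. This is a wording change plus a re-run of one table. It should be made before database lock, when the SAP is to be final; a later change would have to be explained in the clinical study report.
2. Check CRF v3.0 for where and in whom mRS is recorded. Limit the change and shift table to those time points and subjects, and show the number scored in each row. If mRS is recorded only to grade strokes, present day 30 and day 90 for those subjects. This too is SAP wording.
3. If the eCRF does collect mRS at visits, reconcile the protocol's schedule with it at the next amendment. That is a protocol change under Protocol section 14, with submission to the ethics committee, so it costs more than a SAP edit and does not justify an amendment by itself.
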